**A SAE is defined as any untoward medical occurrence that, at any dose:**

**a. Results in death**

**b. Is life-threatening**

The term 'life-threatening' in the definition of 'serious' refers to an event in which the participant was at risk of death at the time of the event. It does not refer to an event, which hypothetically might have caused death, if it were more severe.

**c. Requires inpatient hospitalization or prolongation of existing hospitalization**

- In general, hospitalization signifies that the participant has been detained (usually involving at least an overnight stay) at the hospital or emergency ward for observation and/or treatment that would not have been appropriate in the physician's office or outpatient setting. Complications that occur during hospitalization are AEs. If a complication prolongs hospitalization or fulfills any other serious criteria, the event is serious. When in doubt as to whether "hospitalization" occurred or was necessary, the AE should be considered serious.
- Hospitalization for elective treatment of a pre-existing condition that did not worsen from baseline is not considered an AE.

**d. Results in persistent disability/incapacity**

- The term disability means a substantial disruption of a person's ability to conduct normal life functions.
- This definition is not intended to include experiences of relatively minor medical significance such as uncomplicated headache, nausea, vomiting, diarrhea, influenza, and accidental trauma (eg, sprained ankle) which may interfere with or prevent everyday life functions but do not constitute a substantial disruption.

**e. Is a congenital anomaly/birth defect****f. Other important medical event**

- Medical or scientific judgment should be exercised in deciding whether expedited reporting is appropriate in other situations such as important medical events that may not be immediately life-threatening or result in death or hospitalization but may jeopardize the health of the participant or may require intervention to prevent one of the other outcomes listed in the above definition. These important medical events should also usually be considered serious.
- Examples of such events are intensive treatment in an emergency room or at home for allergic bronchospasm, blood dyscrasias or convulsions that do not result in hospitalization, or development of drug dependency or drug abuse, new-onset diabetes or autoimmune disease.

**Note:** *Serious* and *severe* are not synonymous. The term *severe* is often used to describe the intensity of a specific event as corresponding to Grade 3. This is not the same as *serious*, which is based on participant/event outcome or action criteria usually associated with events that pose a threat to a participant's life or functioning.

### 10.3.3 Recording and Follow-Up of AE and/or SAE

#### AE and SAE Recording

- When an AE/SAE occurs, it is the responsibility of the Investigator to review all documentation (eg, hospital progress notes, laboratory reports, and diagnostics reports) related to the event.
- The Investigator will then record all relevant AE/SAE information in the CRF.
- It is not acceptable for the Investigator to send photocopies of the participant's medical records to the Sponsor in lieu of completion of the CRF pages.
- There may be instances when copies of medical records for certain cases are requested by the Sponsor. In this case, all participant identifiers, with the exception of the participant number, will be redacted on the copies of the medical records before submission to the Sponsor.
- The Investigator will attempt to establish a diagnosis of the event based on signs, symptoms, and/or other clinical information. Whenever possible, the diagnosis (not the individual signs/symptoms) will be documented as the AE/SAE.

#### Assessment of Causal Relationship

By convention, all AEs reported at the injection site (whether solicited or unsolicited) and all solicited systemic AEs are considered to be related to the study intervention and therefore are referred to as reactions and do not require the Investigator's opinion on relatedness.

- Causal relationship of unsolicited systemic AEs and SAEs will be recorded as follows:
  - For non-serious unsolicited systemic AEs (except for non-serious AESIs), relationship to study intervention will usually be assessed by the Investigator only.
  - For SAEs and non-serious AESIs, relationship to study intervention will be assessed by both the Investigator and the Sponsor. Sponsor assessment is entered in the GPV database only.
  - For SAEs only, the causal relationship to study procedures (related/not related to study procedures) will be assessed by both the Investigator and the Sponsor. Sponsor assessment is entered in the GPV database only.
- The Investigator will assess the *causal relationship* between each unsolicited systemic AE and the study intervention administereda as either *not related* or *related*, based on the following definitions:
  - Not related – The AE is clearly/most probably caused by other etiologies such as an underlying condition, therapeutic intervention, or concomitant therapy; or the delay between vaccination and the onset of the AE is incompatible with a causal relationship; or the AE started before the first vaccination (screening phase, if applicable)

a Study intervention administered can correspond to either the investigational product or other products when no investigational product is administered at the visit

- Related – There is a “reasonable possibility” that the AE was caused by the study intervention administered, meaning that there is evidence or arguments to suggest a causal relationship
- The Investigator will use clinical judgment to determine the relationship.
- Alternative causes, such as underlying disease(s), concomitant therapy, and other risk factors, as well as the temporal relationship of the event to study intervention administration will be considered and investigated.
- The Investigator will also consult the IB and/or Product Information, for marketed products, in his/her assessment.
- For each AE/SAE, the Investigator **must** document in the medical notes that he/she has reviewed the AE/SAE and has provided an assessment of causal relationship.
- There may be situations in which an SAE has occurred and the Investigator has minimal information to include in the initial report to the Sponsor. However, it is very important that the Investigator always make an assessment of causal relationship for every event before the initial transmission of the SAE data to the Sponsor.
- The Investigator may change his/her opinion of causal relationship in light of follow-up information and send a SAE follow-up report with the updated causal relationship assessment.
- The causal relationship assessment is one of the criteria used when determining regulatory reporting requirements.

#### **Follow-up of AEs and SAEs**

- The Investigator is obligated to perform or arrange for the conduct of supplemental measurements and/or evaluations as medically indicated or as requested by the Sponsor to elucidate the nature and/or causal relationship of the AE or SAE as fully as possible. This may include additional laboratory tests or investigations, histopathological examinations, or consultation with other health care professionals.
- If a participant dies during participation in the study or during a recognized follow-up period, when available the Investigator will provide the Sponsor with a copy of any post-mortem findings including histopathology.
- New or updated information will be recorded in the originally completed CRF.
- The Investigator will submit any updated SAE data to the Sponsor within 24 hours of receipt of the information.
- Adverse events likely to be related to the study intervention, whether serious or not, that persist at the end of the study will be followed-up by the Investigator until their complete disappearance or the stabilization of the participant’s condition. The Investigator will inform the Sponsor of the date of final disappearance of the event or the date of “chronicity” establishment.

### 10.3.4 Reporting of SAEs

#### SAE Reporting to the Sponsor via an Electronic Data Collection Tool

- The primary mechanism for reporting an SAE to the Sponsor will be the electronic data collection tool.
- If the electronic system is unavailable, then the site will use the paper SAE data collection tool (see next section) in order to report the event within 24 hours. The site will enter the SAE data into the electronic system as soon as it becomes available.
- After the study is completed at a given site, the electronic data collection tool will be taken off-line to prevent the entry of new data or changes to existing data.
- If a site receives a report of a new SAE from a study participant or receives updated data on a previously reported SAE after the electronic data collection tool has been taken off-line, then the site can report this information on a paper SAE form (see next section).
- Details regarding SAE reporting can be found in the Operating Guidelines.

#### Safety Emergency Call

If, as per the Investigator's judgment, a participant experiences a medical emergency, the Investigator may contact the Sponsor's RMO for advice on how to address any study-related medical question or problem. If the RMO is not available, then the Investigator may contact the Call Center—available 24 hours a day, 7 days a week—that will forward all safety emergency calls to the appropriate primary or back-up Sanofi Pasteur contact, as needed. The toll-free contact information for the Call Center is provided in the Operating Guidelines.

This process does not replace the need to report an SAE. The Investigator is still required to follow the protocol-defined process for reporting SAEs to the GPV Department.

In case of emergency code-breaking, the Investigator is required to follow the code-breaking procedures described in [Section 6.3.2](#).

### **10.3.5 Assessment of Intensity**

The Investigator will make an assessment of intensity for each AE reported during the study. An intensity grade will be assigned to each AE. The intensity grading scales used in this study are adapted from the “FDA Guidance for Industry: Toxicity Grading Scale for Healthy Adult and Adolescent Volunteers Enrolled in Preventive Vaccine Clinical Trials, September 2007”.

#### **10.3.5.1 Tables for Clinical Abnormalities**

##### **10.3.5.1.1 Solicited AR Intensity Grading Scale**

**Table 10.2: Solicited injection site reactions: terminology, definitions, and intensity scales**

CRF term (MedDRA lowest level term [LLT])	Injection site pain	Injection site erythema	Injection site swelling
Diary card term	Pain	Redness	Swelling
Definition	Pain either present spontaneously or when the injection site is touched or injected limb is mobilized	Presence of a redness including the approximate point of needle entry	Swelling at or near the injection site Swelling or edema is caused by a fluid infiltration in tissue or cavity and, depending on the space available for the fluid to disperse, swelling may be either soft (typically) or firm (less typical) to touch and thus can be best described by looking at the size of the swelling
Intensity scale*	
CRF: Grade 1: A type of adverse event that is usually transient and may require only minimal treatment or therapeutic intervention. The event does not generally interfere with usual activities of daily living. Grade 2: A type of adverse event that is usually alleviated with additional therapeutic intervention. The event interferes with usual activities of daily living, causing discomfort but poses no significant or permanent risk of harm to the research participant. Grade 3: A type of adverse event that interrupts usual activities of daily living, or significantly affects clinical status, or may require intensive therapeutic intervention.
 
Diary card: Grade 1: No interference with usual activities Grade 2: Some interference with usual activities Grade 3: Significant; prevents usual activities
	
Grade 1: <math>\geq 25</math> to <math>\leq 50</math> mm Grade 2: <math>\geq 51</math> to <math>\leq 100</math> mm Grade 3: <math>> 100</math> mm
	
Grade 1: <math>\geq 25</math> to <math>\leq 50</math> mm Grade 2: <math>\geq 51</math> to <math>\leq 100</math> mm Grade 3: <math>> 100</math> mm

MedDRA: Medical Dictionary for Regulatory Activities

\* For the subjective reaction of pain, participants will record the intensity level (Grade 1, 2, or 3) in the diary card. For the measurable reactions of redness and swelling, they will record just the size of the reaction, and the classification as Grade 1, 2, or 3 will be assigned at the time of the statistical analysis.

**Table 10.3: Solicited systemic reactions: terminology, definitions, and intensity scales**

CRF term (MedDRA lowest level term [LLT])	Fever	Headache	Malaise	Myalgia	Arthralgia	Chills
Diary card term	Temperature	Headache	Feeling unwell or feeling tired	Muscle aches and pains	Joint pain	Chills
Definition	Elevation of temperature to $\geq 38.0^{\circ}\text{C}$ ( $\geq 100.4^{\circ}\text{F}$ )	Pain or discomfort in the head or scalp. Does not include migraine.	General ill feeling. Malaise is a generalized feeling of discomfort, illness, or lack of well-being that can be associated with a disease state. It can be accompanied by a sensation of exhaustion or inadequate energy to accomplish usual activities.	Muscle aches and pains are common and can involve more than one muscle at the same time. Muscle pain can also involve the soft tissues that surround muscles. These structures, which are often referred to as connective tissues, include ligaments, tendons, and fascia (thick bands of tendons).  Does not apply to muscle pain at the injection site which should be reported as injection site pain.	Pain in a joint or joints	Sensation of cold

CRF term (MedDRA lowest level term [LLT])	Fever	Headache	Malaise	Myalgia	Arthralgia	Chills
Intensity scale*	Grade 1: $\geq 38.0^{\circ}\text{C}$ to $\leq 38.4^{\circ}\text{C}$ , or $\geq 100.4^{\circ}\text{F}$ to $\leq 101.1^{\circ}\text{F}$	CRF: Grade 1: A type of adverse event that is usually transient and may require only minimal treatment or therapeutic intervention. The event does not generally interfere with usual activities of daily living.	CRF: Grade 1: A type of adverse event that is usually transient and may require only minimal treatment or therapeutic intervention. The event does not generally interfere with usual activities of daily living.	CRF: Grade 1: A type of adverse event that is usually transient and may require only minimal treatment or therapeutic intervention. The event does not generally interfere with usual activities of daily living.	CRF: Grade 1: A type of adverse event that is usually transient and may require only minimal treatment or therapeutic intervention. The event does not generally interfere with usual activities of daily living.	CRF: Grade 1: A type of adverse event that is usually transient and may require only minimal treatment or therapeutic intervention. The event does not generally interfere with usual activities of daily living.
	Grade 2: $\geq 38.5^{\circ}\text{C}$ to $\leq 38.9^{\circ}\text{C}$ , or $\geq 101.2^{\circ}\text{F}$ to $\leq 102.0^{\circ}\text{F}$	Grade 2: A type of adverse event that is usually alleviated with additional therapeutic intervention. The event interferes with usual activities of daily living, causing discomfort but poses no significant or permanent risk of harm to the research participant.	Grade 2: A type of adverse event that is usually alleviated with additional therapeutic intervention. The event interferes with usual activities of daily living, causing discomfort but poses no significant or permanent risk of harm to the research participant.	Grade 2: A type of adverse event that is usually alleviated with additional therapeutic intervention. The event interferes with usual activities of daily living, causing discomfort but poses no significant or permanent risk of harm to the research participant.	Grade 2: A type of adverse event that is usually alleviated with additional therapeutic intervention. The event interferes with usual activities of daily living, causing discomfort but poses no significant or permanent risk of harm to the research participant.	Grade 2: A type of adverse event that is usually alleviated with additional therapeutic intervention. The event interferes with usual activities of daily living, causing discomfort but poses no significant or permanent risk of harm to the research participant.

CRF term (MedDRA lowest level term [LLT])	Fever	Headache	Malaise	Myalgia	Arthralgia	Chills
	Grade 3: $\geq 39.0^{\circ}\text{C}$ or $\geq 102.1^{\circ}\text{F}$	Grade 3: A type of adverse event that interrupts usual activities of daily living, or significantly affects clinical status, or may require intensive therapeutic intervention. Diary card: Grade 1: No interference with usual activities Grade 2: Some interference with usual activities Grade 3: Significant; prevents usual activities	Grade 3: A type of adverse event that interrupts usual activities of daily living, or significantly affects clinical status, or may require intensive therapeutic intervention. Diary card: Grade 1: No interference with usual activities Grade 2: Some interference with usual activities Grade 3: Significant; prevents usual activities	Grade 3: A type of adverse event that interrupts usual activities of daily living, or significantly affects clinical status, or may require intensive therapeutic intervention. Diary card: Grade 1: No interference with usual activities Grade 2: Some interference with usual activities Grade 3: Significant; prevents usual activities	Grade 3: A type of adverse event that interrupts usual activities of daily living, or significantly affects clinical status, or may require intensive therapeutic intervention. Diary card: Grade 1: No interference with usual activities Grade 2: Some interference with usual activities Grade 3: Significant; prevents usual activities	Grade 3: A type of adverse event that interrupts usual activities of daily living, or significantly affects clinical status, or may require intensive therapeutic intervention. Diary card: Grade 1: No interference with usual activities Grade 2: Some interference with usual activities Grade 3: Significant; prevents usual activities

MedDRA: Medical Dictionary for Regulatory Activities

\* For all reactions but fever, participants will record the intensity level (Grade 1, 2, or 3) in the diary card. For fever, they will record the body temperature, and the classification as Grade 1, 2, or 3 will be assigned at the time of the statistical analysis based on the unit used to measure the temperature and the intensity scale.

***Important Notes for the Accurate Assessment of Temperature:***

Participants are to measure body temperature once per day, preferably always at the same time. The optimal time for measurement is the evening, when body temperature is the highest. Temperature is also to be measured at the time of any apparent fever. The observed daily temperature and the route of measurement are to be recorded in the DC, and the highest temperature will be recorded by the site in the CRF. The preferred route for this study is oral.

**10.3.5.1.2 Unsolicited AE Intensity Grading Scale**

For measurable unsolicited AEs that are part of the list of solicited reactions, the corresponding scale for solicited reactions will be used (see [Section 10.3.5.1.1](#)).

All other unsolicited AEs will be classified according to the following intensity scale:

- Grade 1
  - CRF: A type of adverse event that is usually transient and may require only minimal treatment or therapeutic intervention. The event does not generally interfere with usual activities of daily living.
  - DC: No interference with usual activities.
- Grade 2
  - CRF: A type of adverse event that is usually alleviated with additional therapeutic intervention. The event interferes with usual activities of daily living, causing discomfort but poses no significant or permanent risk of harm to the research participant.
  - DC: Some interference with usual activities.
- Grade 3
  - CRF: A type of adverse event that interrupts usual activities of daily living, or significantly affects clinical status, or may require intensive therapeutic intervention.
  - DC: Significant; prevents usual activities.

**10.3.5.2 Tables for Laboratory Abnormalities**

The pre-defined intensity thresholds for laboratories abnormalities are shown in [Table 10.4](#).

**Table 10.4: Intensity thresholds for laboratory abnormalities**

Endpoint	Mild (Grade 1)	Moderate (Grade 2)	Severe (Grade 3)
Above normal WBC – cell/mm 	10,800 – 15,000	15,001 – 20,000	≥ 20,001
Below normal WBC – cell/mm 	2,500 – 3,500	1,500 – 2,499	≤ 1,499
Hemoglobin (Female) – gm/dL	11.0 – 12.0	9.5 – 10.9	≤ 9.4
Hemoglobin (Female) (Change from baseline value) – gm/dL	Any decrease – 1.5	1.6 – 2.0	≥ 2.1
Hemoglobin (Male) – gm/dL	12.5 – 13.5	10.5 – 12.4	< 10.5
Hemoglobin (Male) (change from baseline value) – gm/dL	Any decrease – 1.5	1.6 – 2.0	≥ 2.1
Platelets decreased – cell/mm 	125,000 – 140,000	100,000 – 124,000	≤ 99,000
Absolute neutrophil decrease – cell/mm 	1,500 – 2,000	1,000 – 1,499	< 999
Absolute lymphocyte decrease – cell/mm 	750 – 1,000	500 – 749	< 499
Absolute eosinophil – cell/mm 	650 – 1500	1501 - 5000	> 5000
Sodium – Hyponatremia – mEq/L	132 – 134	130 – 131	< 130
Sodium – Hypernatremia – mEq/L	144 – 145	146 – 147	> 148
Potassium – Hyperkalemia – mEq/L	5.1 – 5.2	5.3 – 5.4	> 5.4
Potassium – Hypokalemia – mEq/L	3.5 – 3.6	3.3 – 3.4	< 3.3
Blood Urea Nitrogen (BUN) – mg/dL	23 – 26	27 – 31	> 31 or require dialysis
Creatinine – mg/dL	1.5 – 1.7	1.8 – 2.0	≥ 2.1 or requires dialysis
Glucose – Hyperglycemia (random) – mg/dL	110 - 125	126 - 200	> 200
Total protein – Hypoproteinemia – g/dL	5.5 – 6.0	5.0 – 5.4	< 5.0
LFT (ALT, AST) (Increase by factor)	1.1 – 2.5 x ULN	2.6 – 5.0 x ULN	≥ 5.1 ULN
Alkaline phosphate (Increase by factor)	1.1 – 2.0 x ULN	2.1 – 3.0 x ULN	≥ 3.1 ULN
Bilirubin – with any increase in LFT (Increase by factor)	1.1 – 1.25 x ULN	1.26 – 1.5 x ULN	≥ 1.51 ULN
Bilirubin – with normal LFT (Increase by factor)	1.1 – 1.5 x ULN	1.6 – 2.0 x ULN	≥ 2.1 ULN

Endpoint	Mild (Grade 1)	Moderate (Grade 2)	Severe (Grade 3)
PT – increase by factor (prothrombin time)	1.0 – 1.10 x ULN	1.11 – 1.20 x ULN	1.21 – 1.25 x ULN
PTT – increase by factor (partial thromboplastin time)	1.0 – 1.2 x ULN	1.21 – 1.4 x ULN	1.41 – 1.5 x ULN
Urine - glucose	Trace	1+	2+
Urine - protein	Trace	1+	2+
Urine – blood (microscopic - RBCs per high power field (rbc/hpf)	1 - 10	11 - 50	> 50 and/or gross blood

Abbreviations: ALT, alanine aminotransferase; AST, aspartate aminotransferase; dL, deciliter; gm, gram; L, liter; LFT, liver function test; mEq, milliequivalent; mg, milligram; mm^3, cubic millimeter; PT, prothrombin time; PTT, partial thromboplastin time; RBC, red blood cell; ULN, upper limit of normal; WBC, white blood cell.

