- E20: Platelet count, renal function tests (serum creatinine), liver function tests (alanine aminotransferase [ALT], aspartate aminotransferase [AST], total bilirubin, prothrombin time [PT], partial thromboplastin time [PTT] with international normalized ratio [INR]), screening laboratory results that fall into the range of values that are Grade 1 or greater. For the remaining screening laboratory parameters that fall into the range of values that are Grade 2 or greater OR Grade 1 that are deemed clinically significant in the opinion of the Investigator (Grade 1 values for laboratory parameters other than those specified here and deemed not clinically significant may be enrolled at the Investigator's discretion).
- E21: Positive test for chronic active Hepatitis B surface antigen, Hepatitis B core antibody, Hepatitis C antibody, or human immunodeficiency virus (HIV) antibody, either from testing conducted within 4 weeks prior to enrollment or from blood work collected at screening visit

If the participant has a primary physician who is not the Investigator, the site should contact this physician, with the participant's consent to inform him/her of the participant's participation in the study. In addition, the site should ask this primary physician to verify exclusion criteria relating to previous therapies, such as receipt of blood products or previous vaccines.

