- > 20% of participants experiencing Grade 3 systemic reaction (without concurrent infectious disease) that last for at least 3 days at Grade 3 intensity
- > 20% of participants experiencing Grade 3 solicited injection site pain
- > 20% of participants experiencing Grade 3 unsolicited non serious reactions (reactions not explained by any other possible etiology)
- > 20% of participants with Grade 3 laboratory AE
- > 20% of participants with Grade 2 laboratory AE (reactions not explained by any other possible etiology) and judged by the Investigator to be clinically meaningful
- Any related SAEs or any ICU admission for SARS-CoV-2 infection regardless of relationship to vaccination

A subsequent safety review (CS-ESDR-2) is planned for the Sentinel Cohort participants during which the unblinded SMT will examine the available D22-D30 safety data post-second vaccination including local and systemic AEs, unsolicited AEs, and biological safety laboratory parameters, and all available MAAEs, SAEs, and AESIs for the Sentinel Cohort participants will also be reviewed. If no safety signals or major tolerability concerns are identified during this period in the Sentinel Cohort, then all participants in Cohort 2 will progress to get the second injection (VAC2). If a safety signal or a major tolerability concern is identified at CS-ESDR-2 for the Sentinel Cohort, then Cohort 2 participants for the corresponding dose-level may not receive their second vaccination.

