4.4.1.4 Laboratory Test Results

Biological safety tests (biochemistry, hematology, urinalysis, and coagulation) will be performed at the local laboratory. Biological endpoints will be assessed on samples taken at screening and D09 for all participants, D30 (only applicable for Sentinel Cohort and Cohort 2), and unscheduled visits based on Investigator's judgment, in cases of abnormal safety laboratory results.

The parameters to be evaluated are detailed in Table 10.1 of the protocol.

Endpoints will be defined as either within or outside normal range. Normal ranges for each endpoint will be provided by the study center. The biological safety information will be entered by the site staff in the appropriate CRF forms along with units and normal ranges. In case of out-of-range values, specific endpoints may be rechecked, and additional biological parameters may be evaluated, based on the Investigator's judgement. This complementary safety information will also be entered by the site staff in the appropriate CRF forms along with units and normal ranges.

Any change in the testing equipment using different ranges should be reported on an ongoing basis to the Sponsor so that any value can be interpreted at a given time against the appropriate range of values.

Biological safety endpoints will be assessed on whether or not they reach the pre-defined intensity levels (Grade 1, 2, or 3) for analytes with applicable toxicity grading, as specified in the protocol. Table 10.4 of the protocol contains the pre-defined intensity scales according to which the biological safety parameters will be assessed. If at least 1 of these intensity levels is reached, the Investigator will evaluate the clinical significance of the results and report clinically significant abnormal values as AEs in the CRF.

If an endpoint reaches the pre-defined intensity threshold but is within the normal range provided by the study center, it will be treated as not reaching the intensity threshold.

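### Table 10.4 gives no grade to sodium 148 mEq/L, neutrophils 999/mm³ or lymphocytes 499/mm³, so read literally these values miss exclusion E20, the Grade 2 laboratory alerts and the grade-shift table

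*Protocol*

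**What the plan says.** Protocol Section 10.3.5.2, Table 10.4, prints three grades per laboratory parameter. Four rows matter most here: "Sodium – Hypernatremia – mEq/L", "Absolute neutrophil decrease – cell/mm", "Absolute lymphocyte decrease – cell/mm" and "Platelets decreased – cell/mm". Their bounds are set out under the working. The table's only note is a list of abbreviations.

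The grades are used in four places:

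- **Eligibility (Protocol 5.2.2, E20).** For platelets, creatinine, liver function and coagulation tests, a candidate is excluded for "screening laboratory results that fall into the range of values that are Grade 1 or greater". Other parameters, including sodium, neutrophils and lymphocytes, come under "For the remaining screening laboratory parameters that fall into the range of values that are Grade 2 or greater", or under Grade 1 if the Investigator judges it clinically significant.
- **Sentinel alerts (Protocol 8.4.1 and 8.4.2).** The Complete Sentinel reviews use "> 20% of participants with Grade 3 laboratory AE" and a parallel criterion for Grade 2 results judged clinically meaningful. The ad hoc reviews in 8.4.1 use both grades too, with count thresholds in the initial groups.
- **Halting rule (Protocol 8.4.3).** Among laboratory results, this counts Grade 3 only.
- **Analysis (SAP 4.4.1.4 and 5.1.1.2).** The SAP states that "Table 10.4 of the protocol contains the pre-defined intensity scales according to which the biological safety parameters will be assessed", and it plans a summary of grade shift from baseline.

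The only SAP rule that overrides a grade removes it when the value lies within the study center's normal range. SAP 5.3.3 deals with missing values and with results reported as below or above a limit. Neither assigns a grade to a value that falls between two grades.

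**The concern.** A toxicity scale has to be monotone: a more abnormal value must never rank below a less abnormal one. With gaps between adjacent grades, a rule written as Grade 2 or above catches 147, misses 148 and catches 149.

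At stake are the screening exclusion, the Grade 2 alerts and the shift table, where a programmer would have to improvise or show an abnormal value as ungraded. SAP 4.4.1.4 also ties the Investigator's evaluation of clinical significance to a grade being reached, so an ungraded 148 does not prompt that step under the SAP wording.

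**Working it through.** The documents give no figure to reproduce. The check grades each value by the printed bounds and inequality signs of Table 10.4.

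**Gaps that exist at the printed precision**

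| Row | Grade 2 | Grade 3 | Value on each side | Ungraded |
|---|---|---|---|---|
| Sodium, high (mEq/L) | 146–147 | > 148 | 147 = Grade 2; 149 = Grade 3 | 148 |
| Neutrophils (/mm³) | 1,000–1,499 | < 999 | 1,000 = Grade 2; 998 = Grade 3 | 999 |
| Lymphocytes (/mm³) | 500–749 | < 499 | 500 = Grade 2; 498 = Grade 3 | 499 |

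These bounds are whole numbers, so rounding to a whole number does not close the gap. Other rows show contiguous drafting: hyponatremia runs 130–131 then < 130, and high white cells run 15,001–20,000 then ≥ 20,001.

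**Gaps that depend on reporting precision**

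- Platelets: Grade 1 is 125,000–140,000, Grade 2 is 100,000–124,000 and Grade 3 is ≤ 99,000. Counts of 124,001–124,999 and 99,001–99,999 have no grade, which is 999 + 999 = 1,998 integers. If counts are reported in whole thousands, there is no gap.
- ALT/AST: Grade 1 ends at 2.5 and Grade 2 starts at 2.6 × ULN; Grade 2 ends at 5.0 and Grade 3 starts at 5.1. The documents give no ULN. Assuming 40 U/L, 2.5 × 40 = 100 and 2.6 × 40 = 104, so 101–103 have no grade; 5.0 × 40 = 200 and 5.1 × 40 = 204, so 201–203 have none. Assuming 30 U/L, the gaps are 76–77 and 151–152; assuming 50 U/L, they are 126–129 and 251–254. Rounding to one decimal closes them.

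**What each rule does with sodium**

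| Rule | 147 | 148 | 149 |
|---|---|---|---|
| E20, Grade 2 or above | meets | does not meet | meets |
| Grade 2 alert (if clinically meaningful) | counts | does not count | counted as Grade 3 instead |
| Grade 3 alert | no | no | yes |
| Halting rule, Grade 3 (if its other conditions are met) | no | no | yes |
| Shift table | Grade 2 | no grade | Grade 3 |

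The first, second and last lines lose the worse value. The two Grade 3 lines remain monotone.

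**Two ways to close the sodium row**

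- Grade 3 as ≥ 148: 148 becomes Grade 3.
- Grade 2 as 146–148: 148 becomes Grade 2.

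Either way 148 meets E20. It enters the Grade 3 counts under the first reading only. The documents do not show which was intended.

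**Why one rounding rule for every row would do harm**

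PT, PTT and bilirubin with raised liver tests have cut-offs at two decimals. Rounding everything to one decimal would downgrade results:

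- PT 1.22 → 1.2, from Grade 3 to Grade 2
- PT 1.12 → 1.1, from Grade 2 to Grade 1
- PTT 1.42 → 1.4, from Grade 3 to Grade 2
- Bilirubin with raised liver tests 1.52 → 1.5, from Grade 3 to Grade 2

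**The case against.** The strongest reply is that very little turns on this. Only three single integers are ungraded at the printed precision. The laboratory endpoint in Protocol Table 3.1 is out-of-range results, so a sodium of 148 above the local range is still counted. Protocol 8.3.4 requires the Investigator to review each laboratory report and record clinically relevant changes. SAP Section 1 records that vaccination and enrollment were stopped in September 2021, so E20 and the pause rules no longer steer conduct. All of this stands, and it limits the size of the point.

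It can also be argued that the SAP asks whether a value reaches a grade, so that 148 has reached Grade 2. That reading is possible, but it is not written and it conflicts with a Grade 2 range that ends at 147.

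A reader might infer that the gaps weaken the study's halting rule. The documents do not support that as it stands. The rule counts Grade 3 only, and an event is lost only if the boundary value was meant as Grade 3. A reader might also treat the platelet and ALT/AST gaps as unconditional, or assume that every affected result should be at least Grade 2. Neither follows. Those gaps vanish at the printed precision, and platelets of 124,001–124,999 and ALT of 101–103 U/L (assumed ULN 40) lie between Grades 1 and 2.

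**Conclusion.** The fault is real and minor. Sodium 148, neutrophils 999 and lymphocytes 499 have no grade, and nothing elsewhere in either document supplies one. Further gaps in platelets and ULN multiples exist only if results are graded more finely than each row is printed; the documents are silent on that.

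Read literally, E20, the Grade 2 laboratory alerts and the shift table skip a worse value. An effect on Grade 3 counts is conditional on what the sponsor meant by the boundary. The documents give no frequency for these values; single-integer gaps should catch few results. With enrollment and vaccination ended, the live consequence is mainly the descriptive shift table in the final analysis, plus any later reuse of Table 10.4.

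PT above 1.25 × ULN and PTT above 1.5 × ULN also have no grade, because Grade 3 is capped there. That is a different fault, at the top of the scale, and is not counted among the gaps here.

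**What to change.** 1. Reconcile the bounds in Table 10.4 so that adjacent grades are contiguous and every value beyond the Grade 1 threshold has exactly one grade. The sponsor decides which adjacent grade takes sodium 148, neutrophils 999, lymphocytes 499 and the platelet values between bounds.
2. In SAP 4.4.1.4, apply the same bounds to the final shift table. State that results and ULN multiples are graded at the precision printed in each row: two decimals for PT, PTT and bilirubin with raised liver tests, not one decimal throughout.

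The cost is a few table cells, a sentence or two in the SAP and a small change to the grading program. No new data are needed. SAP version 5.0 already revises Section 4 for the final analysis, so an SAP note is enough for the shift table.
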